### 11.1 Reportable Adverse Event

For this trial, a **reportable adverse event** is defined as:

- Any clinically important untoward medical occurrence in a patient receiving study drug or undergoing study procedures which is different from what is expected in the clinical course of a sarcoidosis patient or,
- Any clinically important, untoward medical occurrence that is thought to be associated with the study drug or procedures, regardless of the “expectedness” of the event for the course of a sarcoidosis patient.

### 11.2 Expected events for sarcoidosis

Expected events for sarcoidosis are untoward clinical occurrences that are perceived by the investigator to occur with reasonable frequency in the day to day care of sarcoidosis patients. Examples of adverse events that are expected in the course of this study include dyspnea upon exertion, arthralgias, myalgias, etc. Such events, which are often the focus of prevention efforts as part of sarcoidosis care, will not be considered reportable adverse events unless the event is considered by the investigator to be associated with the study drug or procedures, or unexpectedly severe or frequent for an individual sarcoidosis patient. All SAEs or clinically significant laboratory abnormalities which, in the opinion of the investigator, may be due to study drug or study procedures will be monitored until complete resolution, until the condition stabilizes, or until the participant is lost to follow-up.

Investigators will report all events that are **serious AND unexpected AND study-related, as defined in Manual of Operations and Procedures**, to the Clinical Coordinating Center by phone, fax or email within 24 hours of becoming aware of event. The local Institutional Review Board must also be notified in a timely manner. The investigator will then submit a detailed written report to the Clinical Coordinating Center and the Institutional Review Board no later than 5 calendar days after the investigator discovers the event.

The Clinical Coordinating Center will report all serious, unexpected, and study-related adverse events to the DSMB, by email, or telephone, within 7 calendar days of the CCC being notified of the event. A written report will be sent to the DSMB within 15 calendar days, and these reports will be sent to investigators for submission to their respective Institutional Review Boards. The DSMB will also review all adverse events during scheduled interim analyses. The Clinical Coordinating Center will distribute the written summary of the DSMB’s periodic review of adverse events to investigators for submission to their respective Institutional Review Boards in accordance with reporting guidelines.

The Clinical Coordinating Center will also determine if the serious adverse event is unexpected for CLEAR therapy. Unexpected is defined as any event not listed in the package insert for the individual antibiotic. If the Clinical Coordinating Center determines that any serious and study-related adverse event is unexpected, the FDA will be notified within 7 calendar days. Such events may also meet the definition of Unanticipated Problems as described below.

Investigators must also report Unanticipated Problems, regardless of severity, associated with the study drug within 24 hours. An unanticipated problem is defined as follows:

### 11.3 Unanticipated Problem (UP):

Unanticipated problem is any incident, experience, or outcome that meets all of the following criteria:

- Unexpected, in terms of nature, severity, or frequency, given the research procedures that are described in the protocol-related documents, such as the IRB-approved research protocol and informed consent document; and the characteristics of the participant population being studied;

- Related or possibly related to participation in the research, in this guidance document, possibly related means there is a reasonable possibility that the incident, experience, or outcome may have been caused by the procedures involved in the research;
- Suggests that the research places participants or others at a greater risk of harm (including physical, psychological, economic, or social harm) than was previously known or recognized.

## 12. Study Mandated Deviations from Assigned Treatment Medication Stop Points.

### 12.1. Definition

- A stop point can only occur after the participant is randomized and denotes the occurrence of an event, which necessitates altering the interventions of the study (i.e., cessation of CLEAR therapy or placebo). Visits and data collection continue after stop points. Before a stop point is declared all possible measures will be taken to reverse the problem necessitating the stop point. If there is a necessary deviation from the randomized intervention, we will minimize the degree of the deviation if at all possible. If possible the participant will resume the intervention at a later time.
- General Stop Points:
  1. Pregnancy
  2. ALT >10x upper limit of normal
  3. Intolerable medication-related toxicity

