### 5.1 Blinding and Randomization

Participants will be randomized to either CLEAR therapy or placebo at a ratio of 1 to 1 stratifying by site and use of prednisone  $\geq 10$  mg or not and using a permuted-block randomization algorithm with random block sizes. Randomization schedules will be generated by a statistician who is not involved with the conduct of the clinical trial. The Vanderbilt Investigational Pharmacy will provide each site with the study drugs and site-specific treatment assignments. The placebos and colored capsules will be obtained by each site. Pills of identical appearance containing antibiotics (each a different color) or placebo will be prepared and dispensed by each site's study pharmacy. A participant's treatment assignment will only be revealed outside the pharmacy if a clinical emergency necessitates unblinding their treatment or if requested by the DSMB. Neither participants, clinical providers, nor those influencing recruitment decisions or interpretation of data will be aware of the treatment that is assigned or the order that treatments will be allocated.

Patients will be considered enrolled upon randomization. Patients receiving any amount of study drug will be considered treated. Patients discontinued from receipt of study drug for any reason, will continue to follow all other protocol requirements for the entire 180 day study period to the extent that the informed consent is still active.

Only the investigational pharmacists and the DSMB will be unblinded to randomization assignments. There are safety issues associated the CLEAR regimen; for example, levaquin and prolongation of the QT interval. If there is a significant safety issue thought related to study drug, all four study drugs within the regimen should be stopped and the patient followed until stabilization or resolution of this issue. Efforts will be made to unblind only individuals not associated with the research and who need to know, such as an attending physician. Should un-blinding of an individual become necessary during the study, the investigator at the clinical site should contact the Vanderbilt Clinical Coordinating Center (CCC) for approval and specific unblinding instructions.

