### **5.3 Study Drug Dosing and Administration:**

The following oral CLEAR medications or matching placebo will be introduced as follows:

Day 0 Start: Azithromycin: 250mg po QD (or 500 3 days/week if toxicity) x 8 weeks *and*  
Ethambutol: 1200 mg po QD for  $\geq 50$ kg; <50kg 800 mg po QD (or 3 days/week if toxicity) x 8 weeks  
Rifampin 600 mg QD or Rifabutin 300mg po QD (or 3 days/week if toxicity) x 16 weeks  
Levaquin: 500 mg po QD (or 3 days/week if toxicity) x 16 weeks

Participants will be allowed to take their regimen three times/week instead of daily (which has been shown to be equally efficacious) if toxicity occurs that is thought to be drug related. In addition, if toxicity warrants, one or more drugs can be discontinued and the participant can continue to participate.

The site PI may also elect to stagger the start of study drugs to help identify which drugs may be eliciting which side effects. The study drugs would be introduced starting with Azithromycin and Ethambutol at the baseline visit (day 0) and introducing Rifampin (or Rifabutin) the following week (day 7), and Levaquin one week later (day 14) using the same dosages as above.

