#### **5.6 Discontinuation of Study Drug Administration**

Treatment will continue for a maximum of 112 doses after study enrollment or 16 weeks post-randomization, whichever comes first. Treatment will be discontinued in the following circumstances:

1. Death
2. Primary care provider or participant request
3. ALT is noted to exceed ten times the upper limit of normal
4. A serious adverse event has occurred and is thought to be related to study drug and in the opinion of the investigator or attending physician warrants discontinuation of the study drug, or any intolerable or unacceptable adverse event (including clinically significant abnormal labs thought to be due to study drug) that in the opinion of the investigator or attending physician warrants discontinuation
5. Positive pregnancy test
6. Non-compliance with the regimen and timing that might result in dropping out from the study

7. Development of an intolerable AE due to study participation as determined by the Investigator, participant, or both.
8. Development of an intercurrent illness, condition, or procedural complication, which would interfere with the participant's continued participation.

Participants who have stopped taking study drugs may continue to participate in the study and will follow the appropriate procedures in the protocol.

Any participant who discontinues treatment for medical reasons, e.g. because of adverse events (AEs) or clinical laboratory abnormalities, should be followed up at medically appropriate intervals in order to evaluate the course and to ensure reversibility or stabilization of the abnormality or event. If a participant fails to return for a scheduled visit, a documented effort must be made to determine the reason. This information should be recorded in the study records.

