#### **9.4 Minimization of Risks**

Federal regulations at 45 CFR 46.111(a) (1) requires that risks to subjects are minimized by using procedures which are consistent with sound research design. There are several elements of study design in the present protocol that meets this human subject protection requirement.

Several of the exclusion criteria prohibit participation of patients who might be at increased risk from the effects of antimycobacterial therapy. For example, patients who have intolerances or allergies to any drug in this regimen, pregnancy, and who are taking medications that may unfavorably interact with a drug in the regimen are excluded. Also, we will monitor for adverse effects to liver and muscle by monitoring ALT. We will stop study medications if the ALT rises to more than 10 times ULN.

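### Section 12.1 puts attempts at reversal before a stop point is declared, while 5.6 (ALT above 10 times ULN, pregnancy) and 9.4 (ALT) stop drug on the event itself

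*Combined protocol and SAP*

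**What the plan says.** Section 12.1 describes a stop point as an event after randomization "which necessitates altering the interventions of the study (i.e., cessation of CLEAR therapy or placebo"). It names three general stop points: pregnancy, ALT above 10 times ULN, and intolerable medication-related toxicity. Of all three it says "Before a stop point is declared all possible measures will be taken to reverse the problem necessitating the stop point". It also asks that any departure from the randomized intervention be kept as small as possible, and adds "If possible the participant will resume the intervention at a later time".

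Section 5.6 lists circumstances in which treatment will be discontinued. Two of them are "ALT is noted to exceed ten times the upper limit of normal" and "Positive pregnancy test". Neither carries a precondition. Follow-up to establish that an abnormality reverses or stabilizes is described for participants who have already discontinued.

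Section 9.4 presents the ALT rule as one of the trial's protections: "We will stop study medications if the ALT rises to more than 10 times ULN". It mentions pregnancy only as an exclusion.

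Two other sections bear on how much of the regimen stops. For a significant safety issue thought to be drug-related, 5.1 says "all four study drugs within the regimen should be stopped and the patient followed until stabilization or resolution of this issue". Under 5.3, "if toxicity warrants, one or more drugs can be discontinued and the participant can continue to participate".

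No section says which of these governs when they differ.

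**The concern.** The same laboratory value, and the same positive pregnancy test, lead to two written sequences. A site working from 5.6 stops drug and then follows the participant. A site working from 12.1 first tries to reverse the problem, then declares the stop point, and looks for a way to resume. Each could say that it followed the protocol.

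This matters most for safety. Section 9.4 offers the ALT stop to ethics committees as a risk-minimizing measure without conditions, and 12.1 attaches a condition to it. For pregnancy, 4.2 excludes pregnant women for lack of safety data, and the exclusion criteria warn that oral contraceptives are not effective with a rifamycin, so a positive test is foreseeable. It also matters for conduct: recorded discontinuations and time on drug could vary with the section a site reads.

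**Working it through.** No sample-size, power or error-rate figure is involved. The ALT threshold is identical in 5.6, 9.4 and 12.1, so the conflict is about sequence and finality, not the cut-off.

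**Sections side by side**

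| Question | 5.6 | 9.4 | 12.1 |
|---|---|---|---|
| ALT above 10 times ULN | Discontinue when noted | Stop study medications | Stop point; reversal attempted before it is declared |
| Pregnancy | Discontinue on a positive test | No stop rule | Stop point; reversal attempted before it is declared |
| Intolerable toxicity | Discontinue on the judgement of those named | No specific rule | Stop point; reversal attempted before it is declared |
| Resumption | Silent | Silent | Resume later if possible, no event exempted |

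**Order of events**

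- 5.6 for both events, and 9.4 for ALT: event, stop, follow up.
- 12.1: event, attempt reversal, declare stop point, resume if possible.

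Since 12.1 equates the stop point with cessation, placing reversal before its declaration places reversal before the formal stop. For ALT and pregnancy this cannot be squared with a rule that acts on the finding itself. For intolerable toxicity there is no clear clash, because 5.6 already leaves that stop to judgement. The contradiction in order therefore covers 2 of the 3 listed stop points.

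**Resumption**

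5.6 says discontinued but not permanently, whereas the per-protocol definition in 7.1.2 does speak of a permanent stop. 12.1 fills a silence here rather than denying an express statement, so this limb is weaker.

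**Gap between scheduled ALT tests (Appendix A)**

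After baseline, chemistry is scheduled at weeks 4, 8 and 16, each within 7 days either way.

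- Nominal gap, week 8 to week 16: 112 − 56 = 56 days.
- Longest gap: (112 + 7) − (56 − 7) = 119 − 49 = 70 days.
- Treatment is capped in 5.6 at 16 weeks after randomization, so dosing from day 49 could run at most 112 − 49 = 63 days.

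These are intervals in a schedule, not predicted exposure.

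**Reach into the analysis**

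The per-protocol set drops participants whose regimen was permanently stopped before 4 weeks. The first on-treatment ALT and pregnancy tests fall at week 4, days 28 − 7 = 21 to 28 + 7 = 35. Only a week 4 visit on days 21 to 27, or an unscheduled test, could produce a stop at one of these events that meets the criterion. Per-protocol is a secondary analysis of the primary endpoint only, and 5.1, 7.2 and 12.1 continue data collection after drug stops.

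**The case against.** The best defence is that 12.1 refers to effort made before the event occurs: the three-times-weekly schedule in 5.3, or the drug holiday and pain management in 5.4. On that reading all three sections agree once ALT passes the threshold. The wording does not support it. The measures are aimed at the problem that necessitates the stop point, and for these two stop points that problem is the listed event itself.

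It can also be said that no study measure exists to reverse a pregnancy, so the sentence may cause no delay there in practice. That is plausible, but 12.1 makes no exception and 5.6 makes no allowance.

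Other parts of the defence stand, and they rule out stronger conclusions that a reader might infer:

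- That 12.1 tells sites to keep dosing. It does not. Continued dosing follows only by inference from cessation coming after the reversal attempt.
- That ALT would go unchecked for 56 to 70 days. Section 11.2 requires clinically significant laboratory abnormalities that may be due to study drug to be monitored until they resolve or stabilize (or the participant is lost to follow-up), although it sets no interval. Trying to reverse a raised ALT also implies measuring it again.
- That 12.2 makes stopping depend on confirmation by the site investigator. It sets when the extra measurements are made.
- That 5.1 and 5.3 flatly contradict each other on one drug or all four. They can be read as tiers, a significant safety issue against lesser toxicity. The tiers are not defined, which justifies a cross-reference but not a separate finding.

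**Conclusion.** The point holds in limited form. The order of stopping and attempted reversal is contradictory for ALT above 10 times ULN (5.6 and 9.4 against 12.1) and for pregnancy (5.6 against 12.1). Whether drug may be restarted is inconsistent, but less sharply.

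A reader might infer that the trial's main result is at risk. The documents do not support that: follow-up continues after drug stops, and only a narrow set of early stops could shift between sites in a secondary analysis. The effect on the primary analysis is likely small. How often either event would occur is not given and cannot be derived, so no count of affected participants is possible.

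The conclusion assumes that 12.1 applies to each event it lists, as written. On that footing, a safety event with two incompatible instructions should be put right before sites rely on either. No view is taken on which clinical rule is correct.

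**What to change.** Reconcile 5.6, 9.4 and 12.1 so that each stop point carries one instruction stating:

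1. whether study drug stops on the finding or after an attempt at reversal;
2. whether it may be resumed and, if so, under what conditions;
3. whether one drug or all four stop, by cross-reference to 5.1 and 5.3.

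Add a sentence saying which section governs if wording elsewhere differs. Say also whether a stop with possible resumption counts as permanent for the per-protocol criterion in 7.1.2. The sponsor's medical lead should decide the clinical content of items 1 to 3; the statistical requirement is only that every site reads the same rule.

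The cost is protocol wording in 12.1, matching cross-references in 5.1, 5.3, 5.6, 7.1.2 and 9.4, and the IRB approval that 10.1 requires for changes. The reconciliation in itself calls for no added participants or procedures.

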### 12.2. Measurements at the Time of a Stop Point

When a Stop Point has been confirmed by Site PI, a measurement of complete metabolic profile, CBC, spirometry for FVC and chest CT radiography (non-contrasted CT), if the participant is not pregnant.

### 12.3. Follow-Up After Stop Point

- Following treatment failures, which determine the primary and main secondary outcomes, participant follow-up will include the following information:
  1. Labs tests including CMP, CBC
  2. Spirometry for FVC
  3. Non Contrasted Chest CT, if the participant is not pregnant.

## Appendix A: Time and Events Schedule

Data Collection: Table. CLEAR II Trial Assessments							
Event	Screening Visit 1	Screening Visit 2	Baseline Visit	Week 4 Visit ± 7 days	Week 8 Visit ± 7 days	Week 16 Visit ± 7 days	Week 24 Visit ± 7 days
Consent	X						
Medical History	X						
Physical Exam	X			X	X	X	X
Pregnancy test (if female)	X			X	X	X	
Blood Chemistry (CMP  ; CBC  )	X			X	X	X	
T cell recognition assay	X			X	X	X	X
Spirometry Test/DLCO		X		X	X	X	X
Chest X-ray		X				X	
6MWT  /Borg Dyspnea Score		X*		X	X	X	X
Questionnaires		X				X	
Bronchoscopy			X			X	
Compliance evaluation				X	X	X	
Adverse Events				X	X	X	X
CLEAR II Therapy Initiation			X				

\* 6MWT should be done 2 times (1 hour apart) at this visit, remaining visits, only once (Exception: if participant is experienced with the 6MWT only 1 is necessary at baseline.)

CMP=Complete metabolic profile; CBC=Complete blood count; 6MWT=Six minute walk test
